### **Power Calculation and Sample Size**

We are seeking IRB approval for  $n=550$  participants enrolled in the study. We provide power calculated for key outcomes below, based on an enrollment of 500 participants ( $n=250$  per arm) to account for attrition. The following assumptions are based on findings from our pilot intervention study. First, at baseline, 37% of participants reported a lifetime history of overdose, and 11% reported an overdose in the past six months. As such, for the primary analyses, we assumed that 20% of participants in the control arm will experience an overdose during the 12-month follow-up period. Second, we conservatively assumed an 80% retention rate in the trial, although we were able to retain 90% of pilot participants.

Given these assumptions, we have >80% power to detect a 50% reduction in overdoses (i.e., the primary endpoint for Aim 1, see Research Strategy section C.9, Figure 6A). Similar effect sizes were assumed for an ED-based overdose prevention intervention, and have been deemed as a benchmark for success by key stakeholders. For the second endpoint in Aim 1 (time to first fatal overdose or ED visit related to an overdose), we conservatively assumed that only 38% of self-reported overdoses would result in death or presentation to

the ED based on previous published data, for a rate of 8 per 100 person-years in the control arm. As

Brown University IRB Amendment Approval: 11/09/2021

Brown University IRB Amendment Approval: 12/13/2021

Brown University IRB Amendment Approval: 11/09/2020

Brown University IRB Amendment Approval: 11/22/2019

Brown University IRB Amendment Approval: 8/10/2020

Brown University IRB Amendment Approval: 10/15/2020

Brown University IRB Amendment Approval: 02/26/2021

Brown University IRB Continuing Review Approval: 03/18/2021

Brown University IRB Amendment Approval: 06/15/2021

Brown University IRB Amendment Approval: 09/01/2021

Brown University IRB Amendment Approval: 10/05/2021

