At the completion of the study, patterns of data missingness will be explored to determine the appropriate assumptions required for each affected variable. Missing covariate data considered to be missing completely at random (MCAR), missing at random (MAR) and/or missing not at random (MNAR) will be handled using multiple imputation in SAS (proc MI procedure). Performed in two stages using chained equations, the model will specify the conditional models for the missing outcome and covariates as "MCAR", "MAR", or "MNAR". First, missing patterns will be tested. Then, imputing procedures will be separated into an "imputation phase", "analysis phase" and a "pooling phase". Finally, models with complete case, available data, and fully imputed data will be compared based on their coefficients, standard errors (SE), and *p*-value for the covariates included in the model.

To examine the effect of missing self-reported outcome data on the results, we will first examine the concordance between the self-reported outcome and the primary endpoints relying on administrative data linkages. If a high degree of correlation is observed (e.g.,  $r > 0.80$ ), we will assume missing self-reported outcome information has a negligible impact on the results. If a lack of concordance is observed, we will conduct stratified analyses by number of completed outcome visits (e.g., zero, one, and two) and also employ imputation-based procedures as noted above.

Second, in an exploratory analysis, we will determine the effect of the intervention on the more severe overdose endpoints, defined as an EMS run for suspected overdose, an ED encounter for drug overdose, or drug overdose death. An unintentional fatal overdose (involving any substance) will be determined through linkage to the Office of the State Medical Examiner (OSME), which is responsible for investigating all accidental deaths. Specifically, as defined previously, cases will be considered confirmed unintentional drug-related overdose fatalities if: (i) the death was pronounced in Rhode Island; (ii) the final manner of death was deemed an accident by the medical

---

 <https://doi.org/10.1016/j.drugpo.2017.05.029>

examiner, and (iii) a drug is listed on the death certificate as the primary cause of death or a significant contributing factor. This analysis will be conducted using the same methodology as described above.

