#### **6. Sample Size Calculations**

We provide power calculations for key outcomes below, based on an enrollment of 500 participants (n=250 per arm). To ensure we have a sufficient number of participants and to account for attrition,

we have received IRB approval to enroll up to 550 if necessary. The following assumptions are based on findings from our pilot intervention study. First, at baseline, 37% of participants reported a lifetime history of overdose, and 11% reported an overdose in the past six months. As such, for the primary analyses, we assumed that 20% of participants in the control arm will experience an overdose during the 12-month follow-up period. Second, we conservatively assumed an 80% retention rate in the trial, although we were able to retain 90% of pilot participants.

Given these assumptions, we have >80% power to detect a 50% reduction in overdoses. Similar effect sizes were assumed for an ED-based overdose prevention intervention, and have been deemed as a benchmark for success by key stakeholders. For the exploratory endpoint in Aim 1 (time to first fatal overdose or suspected overdose resulting in an EMS record), we conservatively assumed that only 38% of self-reported overdoses would result in death or attendance by EMS, based on previously published data, for a rate of 8 per 100 person-years in the control arm. We have  $\geq 80\%$  power to detect a 50% reduction in the hazard of fatal overdose or ED visit for an overdose.

Finally, we used a method to estimate sample size for evaluating mediation by joint testing of both links in an indirect pathway from exposure to mediator to outcome (Aim 2). Given the assumptions described above, we have >80% power to detect a statistically significant mediated effect for a coefficient for exposure on mediator and mediator on outcome of at least 0.8 (i.e., a relative risk of  $\exp[0.8] \cong 2.3$ ), respectively.

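### Agreement between self-report and linked overdose records among those interviewed does not make missing self-report negligible; the SAP should name one missing-outcome analysis instead

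*SAP*

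**What the plan says.** The primary endpoint in SAP section 3 is time to first non-fatal overdose from any of three sources: self-report at the 6- or 12-month visit, the state EMS database, or an emergency department encounter. Participants are followed to their first event or to 15 months after baseline. No censoring at the last completed interview is stated.

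For missing self-report, the SAP first looks at concordance between self-report and the linked endpoints. If the correlation is high (0.80 is given as an example), "we will assume missing self-reported outcome information has a negligible impact on the results". If concordance is lacking, "we will conduct stratified analyses by number of completed outcome visits" (zero, one or two), and the same sentence adds the imputation procedures described just before it. That earlier text covers the missing outcome as well as covariates, and says that "models with complete case, available data, and fully imputed data will be compared based on their coefficients, standard errors (SE"), with covariate p-values as a further criterion. No version is named as the one to be reported.

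The planning figures are in SAP section 6: "we assumed that 20% of participants in the control arm will experience an overdose during the 12-month follow-up period", and "we conservatively assumed that only 38% of self-reported overdoses would result in death or attendance by EMS", "for a rate of 8 per 100 person-years in the control arm". The Protocol's Data and Safety Monitoring Plan (Power Calculation and Sample Size) applies the same percentage to a different source: "only 38% of self-reported overdoses would result in death or presentation to" the emergency department. Both documents assume 80% retention.

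**The concern.** The rule uses a quantity measured in people who were interviewed to settle a question about people who were not. A high correlation shows that linkage picks up many of the overdoses that respondents report. It does not show how many participants lack self-report, whether the arms differ in this, or whether those missing have more overdoses than those seen.

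This bears on the primary endpoint. On the 38% assumption most overdoses would be known only from self-report. As the SAP is written, a participant with no interview and no linked record stays in the risk set to 15 months without an event. Unequal retention would then appear as a difference in overdose between the arms. The SAP itself gives differential attrition as a reason for intention-to-treat analysis.

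The choice of approach is also left until the data are in. That matters more here because SAP section 5 says self-reported outcome events reach the principal investigator and study biostatistician unblinded.

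**Working it through.** **Inputs.** Control risk 0.20 over 12 months; linked share s = 0.38; linked rate 8 per 100 person-years; effect "we have >80% power to detect a 50% reduction in overdoses", so 20% v 10%; 250 per arm; 80% retention (all SAP section 6). Two-sided 0.05 (SAP section 4). Allocation 1:1 (Protocol section 3.1a).

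**1. The plan's own figures reproduce.**
- Retained per arm: 250 × 0.80 = 200.
- z = [0.10 × √200 − 1.96 × √(2 × 0.15 × 0.85)] / √(0.16 + 0.09) = (1.414 − 0.990) / 0.5 = 0.849, so power is 0.802. The stated figure is above 80%.
- The required number is 199 per arm, and 199 / 0.80 = 248.75, so 249 against the planned 250.
- Linked rate: 0.38 × 20 = 7.6 per 100, stated as 8. Converting risk to a rate first gives −ln(0.80) × 38 = 8.5.

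**2. Ceiling on the correlation.** For two yes/no variables per person, with self-report proportion pS and a smaller linked proportion pL, the largest Pearson (phi) correlation is √[pL(1 − pS) / (pS(1 − pL))]. It is reached only if every linked case is also a self-reported case.
- 20% v 7.6%: √[(0.076 × 0.80) / (0.20 × 0.924)] = √(0.0608 / 0.1848) = 0.574.
- 20% v 8%: √(0.064 / 0.184) = 0.590.
- At a pooled risk of 15% the ceiling is 0.585 to 0.601; at 10% it is 0.596 to 0.612.
- If 1%, 2% or 5% of those not self-reporting also have a linked event, 0.574 falls to 0.53, 0.50 or 0.41.
- Simulated chance that the sample correlation exceeds 0.80 under perfect nesting: 0.0000 with 400 interviewed at 15% risk, and 0.0002 with 200 at 20%.

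**3. Capture needed for 0.80.** With nesting, r = √[s(1 − p) / (1 − sp)]. Setting r = 0.80 and p = 0.20 gives s = 0.64 / (0.80 + 0.64 × 0.20) = 0.64 / 0.928 = 0.69, against the assumed 0.38.

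**4. Events unseen when self-report is missing.** If a fraction m has no self-report and linkage captures s, the unseen share of events is m(1 − s).
- m = 0.20 (100 of 500), s = 0.38: 0.20 × 0.62 = 12.4%. Of 50 expected control events (250 × 0.20), 43.8 are seen.
- m = 0.20, s = 0.69 (threshold just met): 0.20 × 0.31 = 6.2%; 46.9 of 50 are seen.
- m = 0.10 (the pilot's 90% retention): 6.2% at s = 0.38 and 3.1% at s = 0.69.

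The correlation depends on s and p. It does not depend on m.

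**5. Unequal retention, no true effect.** The observed risk in an arm with retention R is 0.20 × [R + (1 − R)s]. The unequal retention figures below are assumptions; the documents give none by arm.
- 90% control, 70% intervention: 0.1876 v 0.1628 at s = 0.38, ratio 0.87; 0.1938 v 0.1814 at s = 0.69, ratio 0.94.
- 85% v 75%: 0.93 and 0.97. Reversed, 75% v 85%: 1.07 and 1.03.
- Equal retention leaves the ratio at 1, because the factor cancels.

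All of this takes missingness to be unrelated to overdose within arm. If it is related, the error can be larger or smaller, and r among those interviewed would not show it.

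**6. The other branch.** The number of completed outcome visits is known only after randomisation and may be affected by the intervention. Arms compared within the zero-, one- and two-visit strata are therefore not protected by randomisation. The accompanying imputation is to be labelled MCAR, MAR or MNAR after missingness patterns are tested, but observed data cannot separate MAR from MNAR.

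**The case against.** A reader might infer that the threshold is impossible to meet. The documents do not support that. The value 0.80 is only an example, and neither the type of correlation nor the unit is stated. The 38% is a share of overdoses, not of people, and it is attached to death or EMS in the SAP but to death or the emergency department in the Protocol. No combined EMS and emergency department capture is given. Several readings pass or nearly pass:
- three overdoses per affected person: capture 1 − 0.62³ = 0.76, r = 0.85 (two give 0.75);
- EMS and the emergency department each capturing a separate 38%: 76% in total, r = 0.85;
- correlation of event counts with a variance-to-mean ratio of about 2.9 or more;
- a tetrachoric coefficient.

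Each needs an assumption the documents do not contain, so the fair statement is that the threshold is unlikely to be met under the plainest reading.

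Two other strong readings also fail. The correlation is not uninformative: higher capture does mean fewer lost events (12.4% down to 6.2% above). And the strata do not replace the randomised comparison. The SAP presents them as a way to examine missing data, the primary analysis remains intention-to-treat, and imputation sits alongside. Nor does the SAP say that a version will be selected on the treatment p-value; it mentions covariate p-values.

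A last argument is that if the threshold is rarely met, imputation will usually run anyway. That lowers the practical harm. It does not justify keeping a rule whose conclusion is unsound when met, and it does not supply the missing choice of analysis. It is also true that loss of an interview is not loss of the whole endpoint, since linked events remain, and that the follow-up survey asks about overdose since the last visit, so a later interview can cover a missed one.

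**Conclusion.** The point holds in this form. High correlation among those interviewed reflects linkage capture, but not the amount, arm balance or mechanism of missing self-report, so negligible impact does not follow even above 0.80. At the threshold, with 20% missing, about 6.2% of events are still unseen, and 12.4% at 38% capture. The possible distortion of the risk ratio depends on retention by arm, which is unknown: 0.87 to 1.07 across the illustrations at 38% capture, and none if retention is equal and missingness is unrelated to overdose.

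The ceiling of 0.57 to 0.59 rests on three assumptions: a person-level yes/no correlation, 38% as total linked capture, and that share applied per person. It shows the threshold is unlikely to be met under that reading, not that it cannot be. The remaining gap is that no single missing-outcome analysis is pre-specified, and that within-stratum comparisons by completed visits could be read as treatment effects. This should be corrected before the analysis; it does not invalidate the design.

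**What to change.** In SAP section 3:
- Delete the correlation rule and its conclusion. Concordance can still be reported as a description of linkage capture, with the coefficient and unit stated.
- Always run one named analysis: multiple imputation of the unobserved self-report intervals under MAR, by arm, using baseline covariates and linked events.
- Add a delta-adjusted (MNAR) tipping-point analysis that shows how different the unobserved intervals would have to be, by arm, to change the conclusion.
- Report missing self-report by arm and visit, and give complete-case results as sensitivity only.
- Keep tables by number of completed outcome visits descriptive, with no inference on treatment effect within strata.

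The cost is SAP wording and modest extra programming. Imputation of the missing outcome is already planned, and no new data are needed.

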Experimental arm participants will receive the RAPIDS intervention, which includes education about the dangers of IMF, motivational interviewing to increase willingness to use fentanyl test strips and engage in overdose risk reduction behaviors, hands-on training to use the test strips, and opportunities to plan and role- play how to implement overdose risk reduction behaviors upon receipt of a positive or negative test result. In addition, intervention participants will receive ten test strips for personal use. Motivational interviewing “booster” sessions will occur at 1, 2, and 3 months post-randomization, with additional test strips provided on an as needed basis. In the attention-matched control arm, participants will receive standardized overdose education and naloxone distribution (OEND) training, with attention-control visits at 1, 2, and 3 months.

Participants in both arms will receive a naloxone kit after completion of the first session, and information regarding where to obtain additional naloxone at subsequent visits. Follow-up interviews will occur at 6 and 12 months. The primary endpoint will be the rate of self- reported overdose over the follow-up period. Secondary endpoints (e.g., accidental overdose death and suspected EMS runs for overdose) will be ascertained by data linkage to statewide overdose surveillance databases maintained by the research team. Consistent with recruitment rates in our prior studies, we aim to enroll 20 participants per month starting in Year 1 until target

enrollment is reached.

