**Behavioral Outcomes:** Participants in the intervention arm will be asked a series of questions regarding fentanyl test strip utilization at all follow-up assessments. These questions were used successfully in our pilot study, and include items such as, “Of the 10 tests we gave you, how many tests did you use?” and, “What did you do when you found out your drugs were laced with fentanyl?” As an additional measure of test strip utilization, participants will be asked to return unused tests to the study office. We will also assess motivations for using the test strips, including a desire to avoid IMF-contaminated drugs or purposely identifying fentanyl.

At each time point, participants will be asked about the practices they engage in to avoid accidental overdose. Strategies to avoid overdose include the target overdose risk reduction behaviors:

1. discarding IMF-contaminated drugs,
2. not using alone (and staggering drug use with another person who is able to administer naloxone and call 911 in the event of an overdose), and
3. keeping naloxone nearby.

We will also assess other harm reduction practices, including taking a “tester” or lower initial dose, avoiding injection drug use, and purchasing drugs from a consistent source.

**Standard of Care (Attention-Matched Control Arm).** Existing research suggests that training people who are at risk for overdose and their peers on how to respond when witnessing an overdose is a feasible and effective strategy for preventing overdose death. Given that this represents current overdose prevention practice, participants in the control arm will receive the standardized OEND training that occurs in Rhode Island. This program is based on the common components of many community-based overdose prevention interventions in the US, and includes information on risk factors for overdose, recognizing an overdose, performing rescue breaths, administering naloxone, and recommendations to call 911. **To ensure equivalent attention to the RAPIDS arm, control arm participants will return for retention visits at 1, 2, and 3 months,** and will answer a series of questions regarding substance use and overdose risk behaviors.

**Potential Moderators/Other Key Measures:** The RAPIDS survey instrument will contain additional behavioral, psychological, and clinical assessments asked of everyone in the study. Many of these questions have been piloted successfully in our prior research.

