#### **Assessing intervention efficacy in reducing self-reported overdose (Aim 1, primary endpoint).**

First, in the ITT analysis, we will determine the efficacy of the intervention by comparing self-reported rates of overdose among those assigned to the intervention arm versus the control group. First, we will use logistic regression to determine the independent effect of the intervention on the proportion reporting an overdose over the follow-up period, adjusting for baseline covariates as needed. Second, we will use generalized linear mixed effects models (GLMMs) with a logit link function to examine differences in self-reported overdose rates at each time point by incorporating fixed effects representing time, an intervention assignment indicator, and an interaction term that assesses the significance of the intervention influence over time. Third, in a per-protocol sub-analysis, we will determine the effect of the intervention on self-reported overdoses among those who used the fentanyl test strips.

Per-protocol analyses will be based on principal stratification. Principal stratification is a statistical technique that is used to adjust for a post-treatment variable (e.g., utilization of fentanyl test strips), and treatment effects are estimated within each stratum of that variable. We can then estimate the effect of the intervention in reducing rates of self-reported overdoses, conditional on whether participants used the test strips.

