### 3. Data Analysis Plan

For all analyses, a series of routine procedures will first be conducted to ensure data accuracy/adequacy. Descriptive statistics will provide examination of the variables' distributional properties; if required, data will be transformed to achieve normality. For all analyses, we will adopt an intention-to-treat (ITT) approach to address potential problems inherent in following only intervention completers (e.g., self-selection effects, differential attrition across groups). However, we will conduct a modified ITT (mITT), excluding participants who were randomized but did not receive the intervention. For all analyses, the PI, senior biostatistician, and team of co-investigators/consultants will remain blinded to the assignment of study groups until after the statistical analyses are complete and finalized; however, the PI and Project Director receive unblinded information regarding the primary outcome as they were reported by participants, since it is considered a severe adverse event (SAE) and thus these cases are reported to members of the members of the data safety monitoring board (DSMB) and the institutional IRB.

Prior to conducting statistical analyses described below, we will create two baseline tables: 1) one that compares prognostic characteristics between treatment groups immediately after randomization; and 2) a second that compares prognostic baseline characteristics between treatment groups, stratified by whether they completed both outcome visits, a single outcome visit, or were lost to follow-up (i.e., did not complete either the six or 12 month study visit).

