#### Assessing intervention efficacy in reducing fatal and nonfatal overdose (Aim 1, primary endpoint).

The primary outcome will be **non-fatal overdose**, defined as a composite outcome, consisting of one of the following:

1. A self-reported overdose ascertained at the six and/or 12 month follow-up visits;
2. A non-fatal opioid overdose identified in the Rhode Island EMS database, using a case definition for suspected overdose developed by RIDOH previously;
3. An emergency department encounter for an accidental drug overdose that did not result in death, using a case definition developed by the CDC;

The primary analysis will be conducted using a survival framework, with time to *first* nonfatal overdose—identified through any of the data sources noted above—serving as the primary outcome. For self-reported data, event times will be estimated from SAE reports (in which participants are asked to estimate the date of their overdose). Participants will be right-censored as of the date of the first

---

 <https://www.ncbi.nlm.nih.gov/pmc/articles/PMC7948191/>

outcome event or at the end of the follow-up period, defined as 15 months following the participant's baseline visit.

To account for potential imbalance and to improve statistical efficiency, we will adjust for known or anticipated prognostic variables measured at baseline. These variables will include sociodemographic characteristics (e.g., age, gender identity, race/ethnicity), recent criminal justice involvement, housing instability, and substance use patterns including injection drug use & history of overdose. Variables will be transformed or categorized as necessary to address skewed or imbalanced data. We will also adjust for pre-baseline EMS runs for suspected opioid overdoses and ED encounters for drug overdoses using the case definitions noted above, occurring up to six months prior to the date of the participant's baseline visit.

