In two per-protocol sub-analyses, we will determine the effect of the intervention on the primary study endpoint among those who: (1) reported using fentanyl test strips during at least one intervention visit (months one, two, and three) compared to all participants assigned to the control arm; and (2) participants who completed one, two, and all three intervention visits using an ordinal variable, compared to all participants assigned to the control arm.

Finally, to account for potential treatment contamination (e.g., use of fentanyl test strips in the control arm, lack of use in the treatment arm), we will employ an instrumental variable approach to estimate the contamination-adjusted intention to treat (CA ITT) effect. We will consider 'receipt of treatment' to be self-reported use of fentanyl test strips at months one, two, or three follow-up visits.

Examine whether the treatment effect is mediated by differential uptake of risk reduction behaviors in the intervention arm (Aim 2). If the RAPIDS intervention shows efficacy in reducing overdose rates among the sample (Aim 1), we will explore the extent to which this relationship works through several possible mediators. For mediation analyses, first, we will examine, in multivariable regression models, which mediators, if any, are significantly changed by the intervention (i.e., the rate of change differed by treatment assignment). For those that are significantly impacted by the intervention, we will conduct path analysis using structural equation modeling to determine whether the effect of the intervention on overdose was through the hypothesized mediator(s). Structural equation modeling (SEM) allows for the simultaneous estimation of total, direct, mediated and indirect effects of a causal variable (i.e., the intervention) on the outcome (i.e., overdose) through a set of mediator variables. SEM can handle outcomes and mediators with a variety of distributions (including, Gaussian, Poisson and Binomial). Inferences for indirect effects can be estimated using bootstrapped confidence intervals.

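### The SAP's two per-protocol sub-analyses select on behaviour after randomisation in the intervention arm only, so either can show an effect when the package has none

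*SAP*

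**What the plan says.** SAP section 3 (Data Analysis Plan, Aim 1) defines two per-protocol sub-analyses of the primary endpoint.

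- **Strip use.** The group is intervention participants who reported using strips "during at least one intervention visit (months one, two, and three) compared to all participants assigned to the control arm".
- **Visits.** The group is "participants who completed one, two, and all three intervention visits using an ordinal variable, compared to all participants assigned to the control arm".

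The next paragraph adds a further analysis of strip use: "we will employ an instrumental variable approach to estimate the contamination-adjusted intention to treat (CA ITT) effect". Self-reported strip use at months 1, 2 or 3 counts as receipt of treatment.

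Three other places bear on the point.

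- The opening of SAP section 3 adopts intention to treat "to address potential problems inherent in following only intervention completers (e.g., self-selection effects, differential attrition across groups").
- The Data and Safety Monitoring Plan attached to the protocol (section C1, Aim 1) states: "Per-protocol analyses will be based on principal stratification". The SAP does not mention this method.
- Controls have visits on the same schedule. Protocol section 3.1a describes the control arm "with attention-control visits at 1, 2, and 3 months", and the control-arm description in section 3.1b repeats that "control arm participants will return for retention visits at 1, 2, and 3 months". The follow-up survey asks about recent strip use (item C27) outside its arm-specific sections.

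The SAP lists baseline covariates for the primary analysis. It does not say whether they apply to the two sub-analyses.

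**The concern.** Randomisation makes the two whole arms comparable. It does not make a self-selected part of one arm comparable with the whole of the other. People who use the strips, or who keep every visit, may be more cautious than the rest, or may be at higher risk and more worried. In the first case the comparison with all controls leans towards benefit under no effect; in the second, towards harm.

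The strip-use group is also selected on attendance, because a participant must return at least once in months 1 to 3 to report use. Controls who never return stay in the comparator. This is the hazard that the SAP itself gives as its reason for intention to treat.

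Two secondary results are at stake. An ordinal gradient over visits would read as a dose-response, and nothing in the sub-analysis would separate it from selection. The SAP labels the severe-endpoint analysis and Aim 3 exploratory, but not these two.

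**Working it through.** **The plan's own figure.** SAP section 6 assumes 250 per arm, 80% retention, a 20% control risk and a 50% reduction. A two-sided 5% test of 20% v 10% with 200 per arm has 80.2% power, which agrees with the stated figure of more than 80%. The SAP gives no figure for the sub-analyses.

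**Strip users v all controls, no true effect.** Let u be the share of the intervention arm who use strips and r the ratio of users' to non-users' underlying risk. The documents do not give r; 0.5 to 2 is assumed. With no effect, all controls have the same average risk as the whole intervention arm, so

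apparent RR = r / (u·r + 1 − u).

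Two values of u follow from the pilot, reported in the non-significant-risk justification: 77% of those who returned, and 62 of all 93 enrolled = 67%. The second suits a comparison with every randomised control better.

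| u | r = 0.5 | r = 0.71 | r = 1 | r = 1.41 | r = 2 |
|---|---|---|---|---|---|
| 0.77 | 0.5/0.615 = 0.81 | 0.91 | 1.00 | 1.07 | 2/1.77 = 1.13 |
| 0.67 | 0.5/0.667 = 0.75 | 0.88 | 1.00 | 1.11 | 2/1.667 = 1.20 |

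The columns r = 0.71 and 1.41 are the square roots of 0.5 and 2. They show the result if baseline adjustment removed half of the log gradient, which is also an assumption.

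With 200 per arm and 20% average risk, a pooled two-proportion test at r = 0.5 declares a false benefit with probability 14% (u = 0.77) or 21% (u = 0.67). At r = 2 it declares a false harm with probability 9% or 14%. The nominal rate is 2.5% per tail. With r = 1 it stays at 2.5%.

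**Visits v all controls, no true effect.** Assume that 10/10/20/60% complete 0/1/2/3 visits and that risk changes by a factor r^(k/3) at k visits. Then

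RR at level k = r^(k/3) / Σ share·r^(k/3).

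- r = 0.5 (denominator 0.605): 1.31, 1.04, 0.83 for 1, 2, 3 visits.
- r = 2 (denominator 1.743): 0.72, 0.91, 1.15.

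Each row looks like a dose-response, in opposite directions, and neither reflects any effect. A per-visit estimate also depends on coding that the SAP leaves open: the score given to controls, and where intervention participants with no visits go.

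**Ascertainment can bias the result without any risk gradient.** One component of the endpoint is "A self-reported overdose ascertained at the six and/or 12 month follow-up visits", so someone who misses those visits contributes only linked events. Take 80% retention in controls, and use the SAP's 38% (overdoses leading to death or EMS attendance) as a rough proxy for linkage. Controls then have 0.80 + 0.20 × 0.38 = 0.876 of events captured. If the selected participants were retained at 90% to 100% (assumed), the apparent RR under no effect is 0.938/0.876 = 1.07 to 1/0.876 = 1.14, towards harm.

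**Does using the same rule in both arms help?** In a no-effect simulation where attendance behaved alike in both arms, three-visit attenders compared between arms gave hazard ratios of 0.99 to 1.01 and about nominal error. That is the favourable case. Now suppose that 70% of the intervention arm but 50% of controls complete three visits, with a latent trait that lowers log-hazard by 0.5 and raises the log-odds of attendance by 1.0 per SD (all assumed). The like-with-like hazard ratio is then about 1.09, against about 0.87 for intervention attenders v all controls. The bias is smaller, but its sign has changed.

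**The case against.** The best defence has four parts.

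- **Limited role.** These are named sub-analyses beside an intention-to-treat primary analysis, and no decision in the documents depends on them. This stands, and it limits the weight of the point.
- **Strip use is largely handled.** Under monotonicity and an exclusion restriction, the contamination-adjusted estimate is an effect in compliers, which is a principal-stratum effect. Principal stratification has therefore gone in name but only partly in substance. This stands for strip use, with one caveat: the estimate attributes the whole effect of allocation to strips, while protocol section 3.1b says strip use is not the only route by which the package acts. Nothing comparable covers the visit analysis.
- **Baseline adjustment may be intended.** It may, and it would shrink the bias, as the middle columns show. It cannot remove selection on traits that are not measured.
- **The gradients are assumed.** They are. The calculation shows what can happen, not what will.

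A reader might infer that the sub-analyses will exaggerate benefit, or that the trial's main result is compromised. The documents support neither. The bias can go either way, and the primary analysis keeps everyone as randomised. Nor should one infer that matching on attendance cures the problem, because that holds only if attendance behaves alike in the two arms.

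**Conclusion.** The point holds for the two per-protocol sub-analyses and no further. As written, each restricts one arm on behaviour after randomisation and leaves the other unrestricted, so each can show an effect under a strict null. This is a biased comparison that the SAP specifies, not a missing detail.

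For strip use, the illustrative risk ratio under no effect runs from 0.75 to 1.20 over the two uptake figures, and from 0.88 to 1.11 if half of the log gradient is adjusted away. That is modest beside the 50% reduction for which the trial is powered, but enough to raise the false-positive rate well above nominal. These figures rest on assumed gradients and, for visits, on assumed attendance shares. The visit analysis is the more exposed of the two, because no other planned analysis covers it.

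**What to change.** 1. **Visits.** Classify month 1 to 3 attendance in both arms and compare participants with the same attendance, adjusted for the baseline covariates listed for the primary analysis. This replaces the comparison with all controls. Report attendance by arm, and state that the approach reduces selection bias without removing it and can reverse its sign if attendance differs between arms.
2. **Strip use.** Replace users v all controls with one of two options.
   - Restore the protocol's principal stratification. State the strata (would use strips only if allocated to the intervention, in either arm, or in neither) and the identifying assumptions.
   - Rely on the contamination-adjusted analysis already planned, with its exclusion restriction stated, and do not report it as the effect of strips alone.
3. **Both.** State that the baseline covariates apply, and label the two sub-analyses exploratory and non-randomised.

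The cost is SAP wording and modest programming. No new data are needed, because controls already have the visits and are asked about strip use. The primary analysis does not change. The revised results will still rest on assumptions, but these will be stated.
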